10.0 SPONSOR RESPONSIBILITIES AND RECORDS

10.1 Modification of Protocol

Any amendment to this protocol must be signed and dated by the Sponsor and the Investigator prior to its implementation. In the event the modification has the potential to impact the scientific soundness of the investigational plan or the rights, safety, or welfare of the human subjects involved in the investigation, the modification also will require IRB approval prior to its implementation. Any changes to the investigational plan that affects the rights, safety and welfare of the human subjects will most likely require a modification of the informed consent. Any changes to the informed consent will also require IRB approval prior to implementation, and may require subjects already enrolled in the registry to sign a new informed consent.

10.2 Premature Termination of Registry

The registry may be terminated at any time in the event of the occurrence of serious or unexpected adverse events that are determined by the Sponsor or the Investigator to pose a significant safety concern. In addition, the registry may be terminated at any time in the event of the occurrence of information that indicates that the device will not be commercially viable, or in the event that the Sponsor can no longer fund the registry.

The Sponsor will notify the Investigator in the event of premature termination of the registry. Further registry enrollment will be terminated at that time. Follow-up visits will continue for all enrolled subjects to ensure their safety. All subjects experiencing adverse events will be followed to resolution or until they are considered to be medically stable by the Investigator.

10.3 Serious Adverse Event Reporting

All carotid procedure and device related serious adverse events that are associated with the use of the device will be evaluated in accordance with the protocol and the Sponsor's Incident/Event Reporting SOP. Any serious adverse event that requires a Medical Device Report will be reported by the Sponsor to FDA in accordance with the Sponsor's Medical Device Reporting SOP.

10.4 Sponsor Records

The Sponsor shall maintain complete, accurate and current records for the registry, including the following materials:

- Copies of the approved registry protocol and any revisions;
- All correspondence with the Investigator and site personnel, and the IRB;
- Site information including address and IRB information;
- Investigators' curriculum vitae;
- Registry records including copies of IRB submissions and approvals for the registry, IRB approved consent forms and any modifications (and associated approvals);
- Receipt and maintenance of all data as collected on CRFs in SUGAR COMMUNITY EDITION, electronic data capture system for the registry;
- Reports of device malfunctions and failures; and
- Reports of carotid procedure or device related adverse events, including SAEs, DRSAEs and UADEs.

11.0 DATA MANAGEMENT/DATA ANALYSIS/FINAL REPORT

11.1 DATA MANAGEMENT

The Investigator is responsible for the accurate completion and timely submission of the data collected during this registry. All data from this registry will be entered in SUGAR COMMUNITY EDITION, electronic data capture system. Data will be frequently reviewed to identify inconsistent or missing data and any carotid related adverse events. Any data issues are to be promptly addressed with the Investigator by the Sponsor or designated representative. Clinical procedures will be established to ensure that complete, accurate and timely data are submitted, that protocol requirements are followed and that carotid procedure or device related serious adverse events are correctly reported and investigated, as appropriate. The Investigator is to maintain all source documents as required by the protocol, including laboratory results, supporting medical records, and signed Informed Consent forms.

11.2 DATA ANALYSIS

For continuous variables such as subject age, the mean, standard deviation, median and range will be presented. For categorical variables such as presence of conditions observed under medical history, the number experiencing the condition over the total number completing the registry, the percentage, and the exact 95% confidence interval on the percentage will be presented.

Carotid procedure and device related serious adverse events will be listed and the time course, outcome, severity and possible relationship to the device will be documented.

Time to event analysis, when deemed necessary, will be performed using Kaplan Meier methods with any comparisons done via log-rank testing.

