5.8 REGISTRY EXIT

Subjects will be exited from the registry following their scheduled 24-month follow-up evaluation, or earlier if the subject withdraws from the registry, or his/her participation is discontinued by the Investigator, or death. The date each subject completed the registry per this protocol, or if not, then the date the subject exited from the registry and the primary reason should be recorded. Any subject who experiences a serious carotid and/or device related adverse event that is ongoing at the time of exit will be followed by the physician until the adverse event is resolved or the subject is medically stable in the opinion of the Investigator.

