5.9 DISCONTINUED SUBJECTS

Subjects are considered enrolled once they have signed the informed consent form. There are three categories of discontinued subjects: those who withdraw from the registry prior to any activities related to the treatment procedure; those in whom implantation of the CorMatrix ECM for Carotid Repair does not occur due to clinical concerns at the time of operation; and those who elect to withdraw from the registry after implantation of the CorMatrix ECM device. Discontinued subjects will be followed by the physician until they are considered to be medically stable.

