5.10 SUBJECTS LOST TO FOLLOW-UP

If the Investigator or study coordinator has attempted to contact a subject at least three times within 60 days and received no response, the subject may be considered lost to follow-up. The Investigator or study coordinator will document the minimum of three attempts to contact the subject, including sending a certified letter, and contacting the Sponsor, prior to terminating the subject from the registry.

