6.2 REPORTING OF ADVERSE EVENTS

Carotid procedure and device related adverse events are to be completed at any point from the time the subject is enrolled to the time of exit from the registry. Adverse events are to include carotid procedure and device related adverse events as well as any carotid related clinical findings.

Registry subjects will be instructed to immediately report to the Investigator any carotid related unusual signs or symptoms. The

Investigator will take whatever means are necessary to treat the subject, should an adverse event occur. First consideration will be given to the welfare of the subject rather than the successful completion of the registry. All subjects experiencing a carotid procedure and/or device related adverse event will be followed until their clinical outcome is determined, if at all possible, or until completion of the last follow-up visit, whichever occurs later.

All carotid procedure and/or device related findings must be recorded on the appropriate CRF in SUGAR COMMUNITY EDITION, electronic data capture system. A description of the finding, including the start date, resolution date, action taken, and the outcome should be provided, along with the Investigator's assessment of the relationship between the finding and the device. Subjects' complaints of any carotid related symptoms that are outside the normal pattern for the illness treated should be considered AEs.

All carotid procedure and/or device related AE's shall be followed until the event is resolved or determined by the Investigator to be stable. The investigational site will provide relevant follow-up information to the Sponsor upon request.

All SAEs and UADEs must be immediately reported to the Sponsor, CorMatrix Cardiovascular, via telephone or e-mail within 24 hours of the Investigator becoming aware of the event. A completed "Serious Adverse Event" form must be faxed or express mailed to the Sponsor within five working days of the event. The minimum required data to be recorded for an SAE includes: date of event, type of event, actions taken, outcome and, if appropriate, causality and possible relationship to the device(s) used in this registry. In the case of a DRSAE, when possible, the device involved in the failure or malfunction is to be made available to the Sponsor for analysis.

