11.3 FINAL REPORT

A final report will be prepared by the Sponsor at the conclusion of this registry which will summarize all of the data collected, the parameters of all treatments and all carotid procedure and device related serious adverse events recorded during the registry. Copies of the final report will be provided to the Investigator and IRB.

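### Section 11.2 takes percentages and exact intervals over registry completers only, which distorts rates of death and of any event tied to early exit

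*Combined protocol and SAP*

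**What the plan says.** Section 11.2 reports categorical variables as "the number experiencing the condition over the total number completing the registry, the percentage, and the exact 95% confidence interval on the percentage". Medical history is given as an example of such a variable, not as the limit of the rule. The Executive Summary says the descriptive analyses cover outcomes as well as subject characteristics. No enrolled, implanted, safety or per-visit set is defined anywhere.

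Who counts as a completer follows from section 5.8. Exit comes after the 24-month visit, "or earlier if the subject withdraws from the registry, or his/her participation is discontinued by the Investigator, or death". The site records: "The date each subject completed the registry per this protocol, or if not, then the date the subject exited from the registry", with the main reason. Section 5.9 classes as discontinued "those in whom implantation of the CorMatrix ECM for Carotid Repair does not occur due to clinical concerns at the time of operation", and also those who withdraw before or after implantation. Section 5.10 sets out the contact attempts to be documented "prior to terminating the subject from the registry" when follow-up is lost.

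Events are nonetheless collected "at any point from the time the subject is enrolled to the time of exit from the registry" (section 6.2). For these events, section 11.2 promises a listing of the serious related ones and adds: "Time to event analysis, when deemed necessary, will be performed using Kaplan Meier methods". Section 11.3 says the final report will "summarize all of the data collected".

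**The concern.** Adverse events related to the carotid procedure or the device are the registry's stated outcome measure (section 3.1.1), and fatal events are serious by definition (section 6.1). To complete the registry a subject must survive and stay in it for 24 months. A completer denominator therefore conditions on the future: it removes the subjects who died and anyone whose event led to exit.

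The text does not say whose events form the numerator, and neither possibility works for death. The registry has one arm and a descriptive analysis, so these percentages and intervals are its main quantitative result. Section 8.3.4 foresees their use in publications and regulatory submissions. A reader would have a listing of the events but no sound rate for them.

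**Working it through.** **Inputs from the documents.** The enrolment ceiling is 230 (section 3.2), follow-up is 24 months (section 3.3), and the denominator is completers (section 11.2). The plan states no event rate, dropout rate or precision target, so there is no figure of its own to reproduce.

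**Assumptions, not from the documents.** All 230 subjects are implanted; non-completion is 10%, 20% or 30%; event counts are as shown.

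**Interval.** Exact (Clopper-Pearson) 95% limits for x of n: lower = Beta quantile 0.025 with parameters (x, n − x + 1); upper = Beta quantile 0.975 with parameters (x + 1, n − x). The lower limit is 0 when x = 0.

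**Step 1: death.** A subject who dies before the 24-month visit is never a completer, so the result needs no assumption about relative risk.

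| Assumed case | All implanted | Completers in both | All deaths over completers |
|---|---|---|---|
| 5 deaths, 46 non-completers in total, 184 completers | 5/230 = 2.2% (0.7–5.0) | 0/184 = 0% (0–2.0) | 5/184 = 2.7% (0.9–6.2) |
| 12 deaths plus 46 other exits, 172 completers | 12/230 = 5.2% (2.7–8.9) | 0/172 = 0% (0–2.1) | 12/172 = 7.0% (3.7–11.9) |

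In the second case the completers-only interval excludes the crude rate of 5.2%. With 5, 12 or 23 deaths and 10–30% other exits, the crude rate among all implanted runs from 2.2% to 10.0%. Completers-only is always 0%, with upper limits of 1.8% to 2.6%. All deaths over completers runs from 2.5% (5/202) to 16.7% (23/138).

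**Step 2: a serious carotid event, completers in numerator and denominator.** Take 14 events in 230: 6.1% (3.4–10.0). Let C be completers, N non-completers and r the risk in non-completers relative to completers. Expected events in completers are 14 × C/(C + rN), so the expected completer rate is 14/(C + rN).

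| Non-completion | C, N | r = 1 | r = 2 | r = 4 |
|---|---|---|---|---|
| 10% | 207, 23 | 6.09% | 14/253 = 5.53% | 14/299 = 4.68% |
| 20% | 184, 46 | 6.09% | 14/276 = 5.07% | 14/368 = 3.80% |
| 30% | 161, 69 | 6.09% | 14/299 = 4.68% | 14/437 = 3.20% |

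At 20%, rounding to whole subjects gives 11/184 = 6.0% (3.0–10.4), 9/184 = 4.9% (2.3–9.1) and 7/184 = 3.8% (1.5–7.7). The middle figure is slightly low because 9.33 expected events were rounded to 9. At r = 1 there is no bias, only a loss of precision.

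**Step 3: the same event, all events over completers.** 14/207 = 6.8% (3.7–11.1), 14/184 = 7.6% (4.2–12.4), 14/161 = 8.7% (4.8–14.2). The rate is inflated whatever r is. Because some events belong to subjects outside the denominator, the count is not binomial in that denominator and the interval has no valid coverage.

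**The case against.** The best counter-argument is that the scope is inferred. Both examples in section 11.2 (age and medical history) are baseline variables. Serious related events are handled by a listing and time-to-event data by Kaplan-Meier, and the plan never says outright that event percentages use the completer denominator. All-cause death is not a stated outcome rate and appears only as an exit reason. For non-fatal events, nothing in the protocol makes an event a reason to leave, and section 6.2 keeps subjects with related events under observation. Relative risks of 2 and 4 are assumptions, and at r = 2 with 20% non-completion the shift is about one percentage point, with widely overlapping intervals. There is also no hypothesis or performance goal that a wrong percentage could overturn.

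Part of this stands. The size for non-fatal events is unknown and could be nil under the completers-only reading. The reach of the rule to outcomes is the natural reading rather than an explicit statement. A crude proportion of all implanted subjects is also an imperfect benchmark, because events after loss to follow-up go unseen.

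It does not remove the fault. If the rule covered baseline variables only, outcome percentages would have no denominator at all and section 11.2 would need the same repair. Fatal carotid or device events lie within the stated outcome measure. Following up a reported event does not turn an early exiter into a completer. A listing gives no rate, the final-report summary sets no denominator, and Kaplan-Meier is discretionary, with no endpoint, time point or censoring rule named.

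**Conclusion.** The concern holds, and section 11.2 must be corrected. For death the rule is wrong as written under either reading: 0% by construction, or an inflated figure with an invalid interval. Only one of these faults can apply, and the text does not show which. For non-fatal events, completers-only rates are biased when risk differs between completers and non-completers; in the illustration 6.1% becomes 4.7–5.5% at a twofold risk and 3.2–4.7% at a fourfold risk. Variables unrelated to completion lose only precision. Every size rests on assumed event and dropout rates. The direction of the fault in mortality does not, provided at least one subject dies before completing.

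**What to change.** In section 11.2, replace the completer denominator with stated analysis sets, taking numerator and denominator from the same set:

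1. Baseline variables: all enrolled subjects, with the implanted set also shown.
2. Adverse event and device outcome rates: all implanted subjects. Report separately, with reasons, subjects in whom implantation was planned or attempted but did not take place.
3. Duplex findings: subjects with an evaluable scan at that visit, with n shown.
4. Event rates under incomplete follow-up: make time-to-event estimates at 12 and 24 months the planned method rather than an option, and state the endpoints and the censoring rule. Use Kaplan-Meier for death and for composites that include death, and cumulative incidence with death as a competing event for non-fatal carotid events. These estimates should take precedence over the crude proportions in item 2.
5. Completers only: a supplementary analysis at most.

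The cost is a wording change and a little more analysis. No extra visits or subjects are needed. Exit date and main reason (section 5.8) and event start date (section 6.2) are already required; the case report forms are not shown, so their presence there could not be confirmed. Some rates may look less favourable than under the present rule.

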3.1 OUTCOME MEASURES

3.1.1 Performance: Observe the performance and clinical outcome of the CorMatrix ECM for Carotid Repair for patch angioplasty following carotid endarterectomy. Collected data will include both carotid procedure and device related adverse events to determine device performance data.

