6.0 REPORTING OF ADVERSE EVENTS AND SERIOUS ADVERSE EVENTS

6.1 DEFINITIONS

An “Adverse Event” (AE) is any clinical finding that is an undesired or pathological change in a registry subject as indicated by signs, symptoms, illnesses and events that develop or worsen in severity in association with the registry whether or not thought to be related to the device or procedure. Adverse events include current illness, injuries, side effects, toxicities, allergic reactions, or events that occur or worsen during the course of a clinical study. This registry will only collect carotid procedure and device related adverse events as well as any carotid related clinical findings.

Adverse Events will be classified as Serious Adverse Events (SAEs) if the event:

- is life threatening (even if temporary in nature) or fatal;
- results in permanent impairment of a body function or permanent damage to a body structure;
- requires medical or surgical intervention to preclude permanent impairment of a body function or permanent damage to a body structure; or
- requires or prolongs hospitalization.

Once a clinical finding is noted, and the finding is classified as an AE or SAE, the relationship to the device will be classified as follows:

- Not Related: The event is due to an underlying or concurrent illness or effect of another device, drug or intervention and is not related to the use of the registry device.

- **Possible:** The event has a strong temporal relationship to the use of the registry device, and an alternative etiology is equally or less likely.
- **Probable:** The event has a strong temporal relationship to the use of the registry device, and another etiology is unlikely or significantly less likely.
- **Definite:** An event that can only be attributed to the use of the registry device.

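### The outcome is all related adverse events, but the only analysis written for adverse events is a listing of serious ones, and the general percentage rule divides by completers

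*Combined protocol and SAP*

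**What the plan says.** - **Outcome.** Section 3.1: "Collected data will include both carotid procedure and device related adverse events to determine device performance data". There is no limit to serious events, and the Executive Summary gives the same scope.
- **Collection.** Section 6.1: "This registry will only collect carotid procedure and device related adverse events as well as any carotid related clinical findings". Section 6.2 runs this collection from enrollment to exit.
- **Analysis written for adverse events.** Section 11.2: "Carotid procedure and device related serious adverse events will be listed", with their time course, outcome, severity and possible relationship to the device. No count, denominator or interval is attached.
- **General rules in the same section.** "For categorical variables such as presence of conditions observed under medical history", the plan says that "the number experiencing the condition over the total number completing the registry, the percentage, and the exact 95% confidence interval on the percentage will be" reported. Also: "For continuous variables such as subject age, the mean, standard deviation, median and range will be presented". And: "Time to event analysis, when deemed necessary, will be performed using Kaplan Meier methods", with no event named.
- **Final report.** Section 11.3 promises a summary of everything collected, and the only adverse events it names are "all carotid procedure and device related serious adverse events recorded during the registry".
- **Executive Summary, statistical analysis row.** Outcomes are included in the descriptive analyses, in no stated form.

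**The concern.** The outcome covers all related events, while the analysis and report sections name only serious ones. A reader looking for the rule that turns the outcome into a result finds a listing, which has no rate.

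If the general percentage rule is used instead, a second problem appears. Subjects who die or leave early are not completers, so a fatal event is outside the calculation by construction. For a device registry, these are among the subjects whose experience matters most.

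Restenosis shows the practical effect. Section 1.1 gives restenosis as a drawback of other patch materials, Section 7.1 lists recurrent stenosis as a risk, and Sections 5.4 to 5.7 require imaging at four follow-up visits. Yet no section defines restenosis, gives a threshold, or says how its frequency will be reported.

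Section 8.3.4 allows the results to go to publications and regulators. Without a stated numerator, denominator and time point, these could be chosen after the data are seen.

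**Working it through.** The plan states no event rate or precision target, so there is no figure to reproduce. The check has two parts.

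**1. Does any rule commit to a rate for the outcome?**

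| Provision | Covers non-serious events? | Commits to a rate? |
|---|---|---|
| 11.2, adverse event sentence | No | No, a listing |
| 11.2, categorical rule | Yes, by inference; its one example is medical history | Yes, over completers |
| 11.2, continuous rule | Could cover percent stenosis | No, not an incidence |
| 11.2, Kaplan-Meier | Possibly; no event named | No, optional |
| 11.3, final report | Yes, through the summary of all data | No |
| Executive Summary | Yes, as outcomes | No |

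Only the categorical rule yields a rate.

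**2. What does its denominator do?**

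Section 5.8 separates subjects who complete the 24-month evaluation from those who exit earlier through withdrawal, discontinuation by the investigator, or death. Section 5.10 adds termination for loss to follow-up. None of the early exits is a completer.

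Inputs:
- n = 230 is the enrollment cap in Section 3.2, taken here as the number implanted (assumption).
- x = 12 subjects with a related event (assumption).
- Completion of 80% or 70% (assumptions): 0.80 × 230 = 184 and 0.70 × 230 = 161.

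The exact (Clopper-Pearson) 95% interval for x of n has lower limit equal to the 0.025 quantile of Beta(x, n − x + 1) and upper limit equal to the 0.975 quantile of Beta(x + 1, n − x).

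| Subjects counted | Rate | Exact 95% interval |
|---|---|---|
| 12 of 230 implanted | 5.2% | 2.7 to 8.9% |
| 12 of 184 completers (none of the 12 exits early) | 6.5% | 3.4 to 11.1% |
| 6 of 184 completers (six of the 12 exit early) | 3.3% | 1.2 to 7.0% |
| 12 of 161 completers (none exits early) | 7.5% | 3.9 to 12.7% |
| 6 of 161 completers (six exit early) | 3.7% | 1.4 to 7.9% |

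The completers-only rate can err in either direction. It equals the rate among all implanted subjects only if those with events complete as often as the rest: at 80% completion, 0.80 × 12 = 9.6 events among 184 is again 5.2%. Fatal events break that condition, because none of those subjects completes.

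**The case against.** The strongest reply is that the plan already covers the outcome. The medical-history condition in the categorical rule is an example, not a limit, and the occurrence of an adverse event is a categorical variable. The Executive Summary puts outcomes inside the descriptive analyses, and Section 11.3 covers all data collected. On this reading the serious-event listing is an addition to the percentages, not a replacement. Most of this stands.

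A reader might therefore go too far by inferring that non-serious events receive no estimate, or that a compliant report could leave the outcome out. The documents do not support either: the general rule can supply a percentage, and the final report must summarize what was collected. Nor is imaging without any applicable method, since percent stenosis can be summarized under the continuous rule. Asymptomatic restenosis is not always outside the listing either. Under Section 6.1 it is serious if it requires intervention to prevent permanent impairment or damage, or requires hospitalization.

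The reply does not rescue the denominator. The more firmly the general rule is said to govern adverse events, the more directly the completers-only denominator applies to them. The application to adverse events also remains an inference.

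It is also fair to say that this is a descriptive, single-arm registry, so detailed endpoint rules matter less than in a comparative trial. That bears on the priority of the point, not on whether it is correct.

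**Conclusion.** The point holds in this form: the plan does not expressly state an incidence estimate for its own outcome. The one rule that could supply an estimate uses a denominator that excludes subjects who die, withdraw or are lost.

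Its size cannot be read from the documents, which give no event or completion rates. Under the assumptions above, a true 5.2% among implanted subjects could be reported as anything from 3.3% to 6.5% with 80% completing, and from 3.7% to 7.5% with 70% completing, according to whether six or none of the 12 affected subjects exit early. With near-complete follow-up and no fatal events the difference would be small.

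This is an inexpensive improvement to the analysis section, not a defect that prevents the registry from describing device performance. The events and scans are collected in any case.

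**What to change.** **Section 11.2**
- For all related adverse events, overall and by each type listed in Section 7.1, present the number of subjects with at least one event over all implanted subjects, the percentage and the exact 95% interval. Show serious events as a subset and keep their listing.
- A crude 24-month proportion would understate incidence when follow-up is incomplete. For cumulative incidence at 12 and 24 months, commit to the Kaplan-Meier method already named, with censoring at exit, in place of its present conditional use. Count a fatal related event as an event, not as a censored exit.
- Summarize duplex restenosis at each scheduled imaging visit (1 to 3, 6, 12 and 24 months) among subjects scanned, with the number scanned shown. Fix the definition of restenosis in writing before analysis; the documents give none.

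**Section 11.3**
- Delete the word serious, so that all related adverse events are reported.

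**Cost.** Revised wording in two sections, one written definition and a few extra tables. No new data are needed. The reported event burden will look larger than in a listing of serious events alone.

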3.3 REGISTRY DURATION/FOLLOW-UP

All subjects enrolled in this registry will be evaluated preoperatively and followed from their treatment date through 24-months postprocedure. Subjects will have a baseline standard clinical evaluation and standard follow-up evaluations, including carotid duplex imaging, at 1 to 3-months, 6-months, 12-months, and 24-months postprocedure. If intraoperative completion duplex or other imaging (i.e., CTA, MRA, arteriography) is performed, data should be collected, but this is not mandatory.

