Subjects will have a follow-up evaluation 24 months (\pm 1 month) after the carotid procedure. Information will be collected regarding the subject's health status, medications (anti-platelets, anti-coagulants, anti-arrhythmics, anti-hypertensives, betablockers, and statins) and the occurrence of any carotid and/or device related adverse events. A carotid duplex imaging or approved testing is required and the data will be collected on appropriate CRFs in SUGAR COMMUNITY EDITION, electronic data capture system. Results of any additional anatomic imaging performed should be recorded.

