7.0 RISK/BENEFIT ASSESSMENT

7.1 RISKS TO THE SUBJECT

The possible risks associated with the use of the CorMatrix ECM for Carotid Repair for patch angioplasty after CEA are similar to the risks associated with other patch materials for reconstruction or repair of the carotid artery. Risks associated with the use of the CorMatrix ECM for Carotid Repair include:

- Acute or chronic inflammation (Initial application of the CorMatrix ECM may be associated with transient, mild, localized inflammation)
- Allergic reaction
- Bleeding
- Embolization of ECM
- Infection
- Patch dehiscence
- Pseudoaneurysm
- Recurrent stenosis
- Stroke
- Thrombosis
- Vessel occlusion

The known precautions and warnings are listed in the IFU, included as Attachment 2.

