8.3.3 Deviations from the Investigational Plan

The Investigator must notify the Sponsor and the reviewing IRB of any deviation from the Investigational Plan to protect the life or physical well being of a subject in the case of an emergency. This notice must occur as soon as possible, but in no case longer than five working days after the deviation has occurred. Subjects who do not meet the inclusion/exclusion criteria for the registry may not be enrolled as a deviation; any deviations from the enrollment criteria must receive prior approval from the Sponsor and IRB. Subject visits outside of window will not require a five day notification, but should be reported promptly as a deviation.

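### Does the optional Kaplan-Meier analysis in section 11.2 need a dating rule for findings first seen at scheduled duplex scans?

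*Combined protocol and SAP*

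**What the plan says.** Section 11.2 (Data Analysis) presents categorical results as a count over the number completing the registry, with a percentage and an exact 95% confidence interval. One optional sentence on event times follows: "Time to event analysis, when deemed necessary, will be performed using Kaplan Meier methods with any comparisons done via log-rank testing". It names no event, event date, censoring date or time point.

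Findings that can surface at a scan are within scope. Section 3.3 schedules follow-up evaluations "including carotid duplex imaging, at 1 to 3-months, 6-months, 12-months, and 24-months postprocedure", and sections 5.5 to 5.7 put ±1 month around the last three. Section 7.1 lists "Recurrent stenosis" among the risks, together with vessel occlusion. Section 6.1 states: "This registry will only collect carotid procedure and device related adverse events as well as any carotid related clinical findings". Section 11.3 states: "A final report will be prepared by the Sponsor at the conclusion of this registry which will summarize all of the data collected".

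The nearest text to a dating rule is in section 6.2: "A description of the finding, including the start date, resolution date, action taken, and the outcome should be provided". It does not say what the start date means for a finding without symptoms. The draft case report forms (Attachment 3) are not in the supplied text and may define it. Section 5.8 ends participation at the 24-month evaluation.

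**The concern.** A silent restenosis is known only to have arisen between the last negative and the first positive scan. If the scan date serves as the event date and negative subjects are censored at their last scan, two artefacts appear.

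- At exactly month 12 or 24, some of the scans due at that visit have not yet been done. Findings that already exist are not counted, and the curve reads low.
- Subjects leave at the 24-month visit, so the risk set empties between months 23 and 25. Each positive scan late in that window is divided by a small number still at risk, which pushes the curve up. If many final scans come early, this inflates month 24 itself as well as the tail.

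At stake would be a published restenosis curve whose 24-month reading partly reflects visit scheduling and whose confidence interval covers the truth less often than stated.

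**Working it through.** The documents give no event rate, power or Kaplan-Meier target, so there is no figure of theirs to reproduce.

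**Inputs from the protocol.** Scan windows of 1–3, 5–7, 11–13 and 23–25 months (5.4 to 5.7); exit at the 24-month visit (5.8); a cap of 230 subjects (3.2).

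**Assumptions, not in the protocol.** Cumulative incidence F of 5% at 12 and 10% at 24 months, linear in between; every finding detected only at scheduled scans; no loss; visits uniform within windows.

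**Month 12.** Nobody leaves before month 23, so the Kaplan-Meier estimate is the simple proportion already found positive.

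- By the 6-month scan: F(6) = 2.5%.
- Half of the 12-month scans fall by month 12, on average at 11.5 months: F(11.5) = 5% × 11.5/12 = 4.79%.
- Reading at month 12: 2.5 + 0.5 × (4.79 − 2.5) = 3.65%. Simulation gives 3.7%.
- Reading at month 13, when the window has closed: F(12) = 5.0%. The shortfall disappears without any dating rule.

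**Month 24.** About 230 × 0.95 = 218 subjects enter the last window without a finding. Of these, (0.10 − 0.05)/0.95 = 0.0526 are positive at the final scan. Every final scan removes a subject, positive or negative. With H(n) = 1 + 1/2 + … + 1/n and r subjects still at risk at month 24, the added cumulative hazard is about 0.0526 × [H(218) − H(r)], and the curve reads 1 − 0.95 × exp(−that increment). The true increment is −ln(0.90/0.95) = 0.0541.

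| Final visits | r | H(218) − H(r) | Increment | Reading at month 24 |
|---|---|---|---|---|
| Uniform | 109 | 0.691 | 0.0364 | 8.4% |
| Strongly early (stipulated) | 27 | 2.073 | 0.109 | 14.8% |
| Strongly late (stipulated) | 191 | 0.132 | 0.0069 | 5.7% |

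Simulation gives 8.3–8.4%, 14.8% and 5.9%. The bias changes sign where H(218) − H(r) = 0.0541/0.0526 = 1.03, that is, when about 1 − exp(−1.03) = 64% of final scans are done by month 24. Below that share the curve reads low; above it, high.

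**End of the curve.** With uniform visits the simulated value has a median of 25%, and the middle half of runs spans 18–37%. It cannot be interpreted, and numbers at risk would show why.

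**Size against noise, uniform visits.** The bias is 5.0 − 3.7 = 1.3 points at month 12 (SD 1.2) and 10.0 − 8.3 = 1.7 points at month 24 (SD 2.0). Coverage of the nominal 95% interval is 92% and 90%.

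**Sensitivity to the onset model.** A constant hazard with 5% at 12 and 9.8% at 24 months gives 3.7% and 8.3%, essentially the same.

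**What dating does not touch.** The crude 24-month proportion is 10.0% with no loss. Kaplan-Meier on nominal visit times gives 4.8–5.2% and 9.8–10.2% for every visit pattern tried, including the skewed ones. Clinical events with a known date, such as stroke, are unaffected.

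**The case for a change.** The strongest case for a change is that duplex imaging is built into every follow-up visit, and section 3.6 selects sites partly for that expertise. Section 8.3.4 foresees publication and regulatory use. The percentages in 11.2 are taken over completers, so Kaplan-Meier is the only named method that would use partial follow-up. A restenosis curve is then a realistic use of the sentence. Scan dates are what a site would probably enter, and under strongly late attendance month-24 coverage falls to 48%. Fixing the rule would cost a few sentences.

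Much of this is correct. The rule is absent from the supplied text, the mechanism follows from the visit windows alone, and the arithmetic holds. What does not follow is that the plan leads to a wrong result. Harm needs three choices that the plan does not make: running the optional analysis, applying it to scan-detected findings, and reading it on actual scan dates at the nominal month. The poor coverage also needs the whole registry to attend late, and nothing in the documents suggests that. The completers denominator is a separate matter that a dating rule would not settle. Nor would such a rule make the curve computable, because no supplied text gives a restenosis threshold.

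**Conclusion.** No change to the plan follows. This is an unstated detail of an optional, descriptive analysis in a single-arm registry, and the sentence already permits the sound choice. An analyst who draws such a curve would ordinarily use nominal visit times, or read month 12 once its window has closed, show numbers at risk, and leave the tail unread.

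With evenly spread visits, even the naive scan-date curve errs by about one standard deviation or less. Larger distortions, 5.9% to 14.8% against a true 10% at month 24, appear only under stipulated skew in attendance. All sizes rest on the assumed 5% and 10% incidence, 230 subjects and no loss; the mechanism does not. The judgement would differ if the plan named restenosis as an endpoint with a Kaplan-Meier rate at a fixed month, or planned a comparison on it. It does neither.
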